10.3 Specific features of the protocol

All serious and non-serious adverse events must be reported in the CRF.

Serious adverse events that do not require the investigator to notify the sponsor

These serious adverse events are only recorded in the "adverse event" section of the case report form. They include the events associated with:

• Normal and natural evolution of the pathology, for example: High blood pressure, headaches except for the first 2 months of corticotherapy Lower limbs edema except for the first 2 months of corticotherapy Gross haematuria

Acute renal failure

Nephrotic syndrome

Special circumstances

Hospitalization for pre-existing pathology

Hospitalization for a medical treatment or scheduled surgery before the research Admission for social or administrative reason

Hospitalization in an emergency department (<12 hours)

• Adverse events likely to be associated with the treatments prescribed as part of the patient's care during the monitoring of the research, for example adverse events related to the prescription of RAS blockers :

Hypotension

Acute renal failure

Glucose metabolism disequilibrium

Serious adverse events that require the investigator to immediately notify the sponsor

The investigator must report all adverse events that meet one of the seriousness criteria below:

1- Death

- 2- Life threatening situation
- 3- Requiring hospitalization or prolonging hospitalization
- 4- Persistent or significant disability or incapacity
- 5- Congenital abnormality or birth defect
- 6- Or any other adverse event considered "medically significant"

The serious adverse events the most related are:

- High blood pressure (systolic blood pressure ≥180 mmHg or diastolic blood pressure ≥120mmHg), headaches and lower limbs edema in the first 2 months of corticotherapy, diabetes, infections, osteoporosis with fracture and cardiac insufficiency.

Other events that require the investigator to immediately notify the sponsor

• In utero exposure

The sponsor must be notified immediately about any pregnancy during which the foetus (from the pre-embryonic stage up to birth) could have been exposed at a given time to an experimental medication, even if the pregnancy is not associated with an adverse event. Notification is required if the exposure involves the mother.

Other events occurring following an interaction between corticosteroids and antihypertensive treatments (Beta blockers and diuretics):

Hyperkalemia (> 6mmol/l)

Torsade de pointes

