A recent meta-analysis, evaluating the effect of steroids in 536 patients with significant proteinuria and preserved renal function, has shown a 68% reduction of a renal composite endpoint (ESRD, doubling serum creatinine and 50% decline of eGFR) in patients treated with steroids⁵. This treatment allowed also a significative reduction of proteinuria. Side effects (diabetes mellitus or impaired glucose intolerance, hypertension, gastrointestinal bleeding, cushingoid features, insomnia, headache, weight gain) were relatively well tolerated. However, most of the statistical power in this meta-analysis was obtained from only 2 Italian studies⁵. In the Pozzi *et al.* study, a 50% increase in serum creatinine had been observed in 9/43 patients treated with steroids vs 14/43 patients treated without steroids²⁹, a beneficial effect similar to the one obtained with RAS blockade only ²⁷ (whereas RAS blockade was not systematic in the Pozzi study). In the other Italian study, about 30% of patients presented with persistent proteinuria >1g/d, suggesting optimal RAS blockade had not been reached³⁰. Then, the beneficial effect of corticosteroids could be less pronounced, if strict RAS inhibition was obtained in controls patients treated without corticosteroids. Consequently, the role of steroids, a treatment with potentially severe side effects, in IgAN remains discussed.

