5.7.3 Terminating part or all of the research

5.7.3.1 Criteria and methods for prematurely terminating all or part of the research by the patient

Any subject can withdraw from participating in the research at any time and for any reason. In case of end stage renal disease (ESRD) or renal transplantation, the subject stay in the research but the patient will not have anymore visits in the protocol. Only infectious AE and SAE will be report.

The investigator can permanently end a subject's participation in the research for any reason that affects the subject's safety or which would be in the subject's best interests.

If the subject is lost to follow-up, the investigator has to make contact with the subject and draw it in the file source to know at least if the subject is alive or died.

If a subject leaves the research prematurely, data relating to the subject can be used.

The case report form must list the various reasons for ending participation in the research:

- □ Explicit withdrawal of consent
- □ Follow- up
- Death
- □ Other

5.7.3.2 Criteria and methods for prematurely terminating all or part of the research by sponsor

AP-HP as sponsor or the Competent Authority (ANSM) can prematurely terminate all or part of the research, temporarily or permanently, in the following situations:

- first of all, if suspected unexpected serious adverse reactions (SUSARs) are seen in an arm being treated or if there is a discrepancy in the serious adverse reactions between the 2 arms, and which require a reassessment of the benefit-risk ratio for the research.
- likewise, if unexpected facts, new information about the product, in light of which the objectives of the research are unlikely to be achieved.
- if it appears that the inclusion objectives are not met.

If the research is terminated prematurely, the decision and justification will be given by the sponsor, AP-HP, to the Competent Authority (ANSM) and to the CPP within 15 days.

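### Protocol section 10.3 exempts serious glucose disturbance from SAE notification but requires immediate notification of diabetes, with no rule to separate the two in steroid-exposed patients

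*Protocol*

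**What the plan says.** Section 10.3 contains two lists.

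- The first is headed "Serious adverse events that do not require the investigator to notify the sponsor". Its events are recorded only in the adverse-event part of the CRF. One of its categories is "Adverse events likely to be associated with the treatments prescribed as part of the patient's care during the monitoring of the research", with RAS blockers as the worked example, and "Glucose metabolism disequilibrium" is an entry there.
- The second covers serious events that must be notified immediately. It requires notification of every event meeting a seriousness criterion, then names those most related: high blood pressure above stated limits, "headaches and lower limbs edema in the first 2 months of corticotherapy, diabetes, infections, osteoporosis with fracture and cardiac insufficiency".

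Section 10.2 obliges the investigator to notify all serious adverse events except those that the protocol lists as exempt. It places notified events in the serious-adverse-event part of the CRF.

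Section 2.2 reports, from a meta-analysis of steroids in this disease: "Side effects (diabetes mellitus or impaired glucose intolerance, hypertension", followed by other effects.

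Section 5.7.3.2 lets the sponsor or the competent authority stop the trial "if there is a discrepancy in the serious adverse reactions between the 2 arms" and the benefit-risk ratio needs reassessment. Section 10.7 states that no DSMB is convened.

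**The concern.** A hospital admission for hyperglycaemia in a patient on prednisone can be described by either entry. If the site calls it diabetes or attributes it to the steroid, it goes to the sponsor at once. If the site calls it a glucose disturbance related to the RAS blocker, it goes only into the adverse-event part of the CRF.

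The exemption is decided by the site's view of causality. Under section 10.6, the sponsor's own causality assessment, which weighs the experimental medication against other treatments, is made on the events reported to it. The site's answer to the causality question therefore determines whether anyone else is promptly asked it. Glucose disturbance is a harm that the protocol itself links to the tested treatment, and no independent board would see an imbalance building up.

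**Working it through.** The point rests on text, and the plan has no figure on it to reproduce. The steps are as follows.

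**1. Does the general rule override the exemption?** No. Section 10.3 says all events meeting a seriousness criterion must be reported, but section 10.2 excepts events that the protocol lists as not needing immediate notification. The exempt list can prevail.

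**2. Is there a rule separating the two entries?**

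| | Exempt entry | Notifiable entry |
|---|---|---|
| Term | Glucose metabolism disturbance | Diabetes |
| Definition or threshold | None | None |
| Link to a drug | Care treatments, e.g. RAS blockers | Serious events most related |
| Corticotherapy window | None | None |

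**3. Does the section separate other overlapping events?** Yes. Headaches and oedema also stand on both lists, and there a time window divides them: "Lower limbs edema except for the first 2 months of corticotherapy" on the exempt list, matched by the first two months of corticotherapy on the notifiable list. Glucose has no such divider.

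**4. Is the RAS-blocker attribution always available?** Yes. Section 7.2.2 gives RAS blockade to all patients, so every steroid-treated patient also has the exempting exposure. Section 4.2.1 makes the trial open-label, so attribution is made with the allocation known. Rescued controls are less clear still: section 7.1 describes the experimental medications as given to the experimental group, while section 7.4.1 gives the same course to controls as rescue.

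**5. How many patients could be affected?** From section 9.1, 61 per group. Steroid-exposed patients number 61 + R, where R is the number of rescued controls.

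- R = 0: 61 + 0 = 61
- R = 61: 61 + 61 = 122

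The range is 61 to 122 of 122.

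**6. How many events might that be?** The protocol gives no rate, so the rates r below are assumptions, applied to the 61 experimental patients. Expected events = 61 × r; chance of at least one = 1 − (1 − r)^61.

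| Assumed r | Expected events | Chance of at least one |
|---|---|---|
| 2% | 1.2 | 71% |
| 5% | 3.1 | 96% |
| 10% | 6.1 | 99.8% |

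These are all serious glucose events, of which only those attributed to the RAS blocker would take the exempt route. With counts this small, one or two rerouted events could change how a between-arm comparison looks.

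**The case against.** The strongest reply is that the exemption is limited by attribution. The glucose entry sits under care treatments, and section 5.5 classes RAS blockade as care and corticosteroids as research treatment. Read strictly, a glucose event attributed to steroids is not exempt, and a site whose steroid-treated patient is admitted with diabetes has an explicit instruction to notify. This stands. It confines the problem to events attributed to the RAS blocker or of unclear cause, but does not remove it, since both drugs are present in every steroid-exposed patient.

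The contrast with headaches and oedema also has limits. Their window belongs to the category for natural disease evolution, which is not defined by drug, and no entry in the care-treatment category carries one. The exact nesting of the list is lost in the extracted text. The contrast shows that the protocol has a device for dividing an overlap, not that its absence here was an oversight.

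Three stronger readings are tempting, and the document does not support them.

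- **The event is hidden from the sponsor.** It is not. Section 10.3 puts all adverse events in the CRF, section 12.5 lets the sponsor's clinical research associate view entries remotely, and section 12.4 provides for checks against source. Fasting glycaemia is measured at D0 hospitalisations and at follow-up visits, and section 9.2 analyses toxicity by treatment received. What can be lost is SAE notification and vigilance review.
- **SUSAR declaration is impaired.** That concerns unexpected reactions. Expectedness is judged against product summaries given only as links, and section 2.2 treats glucose effects as known.
- **About 98 of 122 patients are affected.** This comes from applying the 60% RAS non-response in section 2.2 to 61 controls (61 + 0.60 × 61 = 97.6). That 60% is a three-month figure from an external series, whereas rescue can start as late as M18. It counts exposure, not misrouted events, and is neither an estimate nor an upper bound.

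**Conclusion.** The overlap is real and should be corrected. Section 10.3 gives a serious glucose event in a steroid-exposed patient two possible routes, and the choice rests on an open-label site's attribution. On the exempt route the event bypasses the SAE form and the Vigilance Division's causality assessment, while remaining in the CRF.

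The consequence is a possible understatement of serious steroid reactions in the between-arm comparison of section 5.7.3.2 and in the annual cumulative SAE tabulation of section 10.6. This assumes that both draw on notified events or on the serious-adverse-event part of the CRF; the protocol does not state their source. If steroids raise the rate of serious glucose events, the loss would narrow the difference between arms. The final toxicity analysis is not shown to be affected.

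At least 61 patients are exposed, plus any rescued controls. The number of misrouted events cannot be estimated from the document. The absence of a DSMB makes the notification route matter more. The repair costs almost nothing.

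**What to change.** Reconcile the two entries in section 10.3 so that a serious glucose event in a patient exposed to study or rescue corticosteroids has one notification route, whatever the site's attribution. The section's corticotherapy exception for headaches and oedema is a ready model for the form of words. Its two-month window should not be copied without thought, because the oral course in section 7.1 lasts four months and rescue can begin as late as M18. The Vigilance Division should confirm the wording and the period covered.

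If the trial has started, check whether any serious glucose events have already been recorded as exempt and send them for vigilance assessment.

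The cost is a one-line protocol correction, a memo to sites and possibly a few more SAE forms. Randomisation, sample size and the efficacy analysis are untouched.

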
10.4 Procedures and deadlines for notifying the sponsor

Notification of an SAE must initially be provided in a written report using the special form for reporting SAE. The report must be signed by the investigator.

Each item in the form must be completed by the investigator so that the sponsor can carry out the appropriate analysis.

This initial notification must be followed by one or more detailed follow-up report(s), in writing and signed, within a maximum of 8 days in the case of a fatal or life-threatening event and within 15 days for all other cases.

Whenever possible, the investigator will provide the sponsor with any documents that may be useful (medical reports, laboratory test results, results of additional exams, etc.). These documents must be made anonymous. In addition, the documents must include the following: research acronym, number and initials of the subject, nature and date of the serious adverse event.

Any adverse event will be monitored until fully resolved (stabilisation at a level considered acceptable by the investigator, or return to the previous state) even if the subject has left the trial.

The initial notification, the SAE follow-up reports and all other documents must be sent to the sponsor via fax only to the Vigilance Division of the DRCI, [contact]**.

For this study using e-CRF:

- the investigator completes the SAE notification form in the e-CRF, validates, prints and signs the form before sending it *via* fax.

- if it is not possible to connect to the e-CRF, the investigator will complete, sign and send the SAE notification form. As soon as the connection is restored, the SAE notification form in the e-CRF must be duly completed.

The investigator must comply with all requests from the sponsor for additional information.

For all questions relating to the notification of an adverse event, the Vigilance Division of the DRCI can be contacted via email: [contact]

In utero exposure

The investigator completes the "form for monitoring a pregnancy that developed during a biomedical research" and sends it by fax to the Vigilance Division at **[name]**.

The investigator must monitor the pregnant woman throughout her pregnancy or until the pregnancy is terminated, and must notify the sponsor of the outcome of the pregnancy, using this form.

If the outcome of the pregnancy falls within the definition of a serious adverse event (miscarriage, pregnancy termination, foetal death, congenital abnormality, etc.), the investigator must follow the procedure for reporting SAE.

If the exposure involves the father, the investigator must obtain the mother's permission before collecting information about the pregnancy.

The initial pregnancy notification, the SAE follow-up reports and all other documents must be sent to the sponsor via fax only to the Vigilance Division - of the DRCI, [contact]**.

10.5 Period for notifying the sponsor

The investigator must report all SAE that occur in research subjects:

- After the date of the first procedure specific to the research

- Throughout the period during which the participant is monitored, as determined by the research

10.6 The sponsor's roles

The sponsor, represented by its Vigilance Division, continuously assesses the safety of each experimental medication throughout the research.

Analysis and declaration of serious adverse events

The sponsor assesses:

- the seriousness of all adverse events reported
- the causal relationship of these events with each experimental medication and/or specific medical procedures/exams added by the research and with other possible treatments
- the expected or unexpected nature of these adverse reactions

For serious adverse events related to the experimental medications and which are expected, the SmPC for METHYLPREDNISOLONE 500 mg and Prednisone should be consulted.

All serious adverse events which the investigator and/or the sponsor believe could reasonably have a causal relationship with the experimental medication are considered as suspected adverse reactions.

All suspected unexpected serious adverse reactions (SUSAR) are declared by the sponsor, within the legal time frame, to the Agence Française de Sécurité Sanitaire des Produits de Santé (ANSM, French Health Products Safety Agency) and to the relevant Comité de Protection des Personnes (CPP, ethical committee).

- The initial declaration must be made no later than 7 calendar days after the date on which the serious adverse event occurs in the case of death or of a life-threatening diagnosis.
- The initial declaration must be made no later than 15 calendar days after the date on which the serious adverse event occurs in the case of other serious situations.
- The follow-up declaration must be made no later than 8 days after the 7- or 15-day deadline (depending on the seriousness).

Any suspected unexpected serious adverse reaction must also be declared electronically in the Eudravigilance European database for adverse events due to medications, established by the European Medicines Agency (EMA).

The sponsor must notify all relevant investigators about any data that could adversely affect the safety of the research subjects.

Specific cases of serious adverse events of special interest:

At the request of ANSM, the sponsor may be asked to declare serious adverse events of special interest, in accordance with the same procedures and deadlines as SUSARs.

Analysis and declaration of other safety data

This relates to any safety data or new fact that could significantly alter the assessment of the benefit-risk ratio for the experimental medication, or for the research, or which could lead to the possibility of altering the administration of the experimental medication or altering the conduct of the research.

New facts must be declared to the competent authorities within 15 calendar days of the sponsor becoming aware. Additional relevant information must be sent within an additional 8 days after the 15 day deadline.

Annual safety report

Once a year for the duration of the clinical trial, the sponsor must draw up an annual safety report (Development Safety Update Report - DSUR) which includes, in particular:

- an analysis of the safety of the research subjects

- a description of the patients included in the trial (demographic characteristics, etc.)

- a line listing of suspected serious adverse reactions that occurred during the period covered by the report

- a cumulative summary tabulation of serious adverse events that have occurred since the start of the research

The report must be delivered no later than 60 days after the anniversary of the date on which the ANSM authorised the trial.

10.7 Data Safety Monitoring Board

The Data and Safety Monitoring Board (DSMB) can be established by the sponsor. Its primary mission is to serve as a committee for monitoring safety data. It can have other missions, such as monitoring efficacy data (especially if the protocol includes interim analyses).

The DSMB is mentioned in Article L. 1123-7 of the French Public Health Code.

The sponsor is responsible for justifying the creation or absence of a supervisory committee to the Competent Authority (ANSM) and to the CPP.

For this biomedical research, it has not been considered beneficial to convene a DSMB because this study is a research with low risk (B risk) according the sponsor procedure and the coordinating investigator.

11 DATA MANAGEMENT

11.1 Data collection methods

Information required in the research protocol must be collected in the case report form (CRF) and an explanation must be given by the investigator for each missing data.

Data must be reported in the electronic CRF when they are available, for clinical or paraclinical data.

Correction of discordant data on CRF will be asked through queries. In the CRF, the changes in the data will be tracked.

Anonymization of the patients will ensured using a code number and initials, reported on each needed documents for the research, or by erasing nominative data on copies of source documents.

11.2 Right to access source data and documents

Access to data

In accordance with GCPs:

- the sponsor is responsible for obtaining the permission of all parties involved in the research to guarantee direct access to all locations where the research will be carried out, to the source data, to the source documents and the reports, with the goal of quality control and audit by the sponsor

- the investigators will make available to those in charge of monitoring, quality control and audit relating to the biomedical research the documents and personal data strictly necessary for these controls, in accordance with the legislative and regulatory provisions in force (Articles L.1121-3 and R.5121-13 of the French Public Health Code)

Source documents

Source documents are defined as any original document or object that can prove the existence or accuracy of a piece of information or a fact recorded during the research. These documents will be kept for 15 years by the investigator or by the hospital in the case of a hospital medical file.

In this research, the source documents will be: paper and electronic medical file, nurse file, and anapathology results.

Data confidentiality

Those responsible for biomedical research quality control (Article L.1121-3 of the French Public Health Code) will take all necessary precautions to ensure the confidentiality of information about the experimental medications, the research, the research subjects and in particular the identity of the subjects and the results obtained.

These individuals, as well as the investigators themselves, are subject to professional secrecy (in accordance with the conditions set out in Articles 226-13 and 226-14 of the Penal Code).

During or after the biomedical research, the data collected about the research subjects and sent to the sponsor by the investigators (or any other specialised parties) will be made non-identifying.

Under no circumstances should the names and addresses of the subjects involved be shown.

The sponsor will ensure that each research subject has given permission in writing for access to personal information about him or her which is strictly necessary for the quality control of the research.

